1. PURPOSE OF THE STUDY AND BACKGROUND

1.1. Purpose of the study

To determine the duration of effect of a single dose of Biotène Moisturizing Mouth Spray in subjects who complain of a clinically dry mouth. The effect of the product will be compared to a control spray (water). A secondary objective is to assess how the perception of a dry mouth is related to the severity of actual hyposalivation.

1.2. Background

Xerostomia is a subjective feeling of a dry mouth which may or may not occur with decreased amounts of saliva in the mouth (Furness et al 2011, Sasportas et al. 2013, Jose et al. 2016). Complaints of xerostomia are typically related to resting discomfort and difficulty with functions such as eating and speaking. Xerostomia is commonly a permanent or temporary result of irradiation of salivary glands, autoimmune disease, smoking, alcohol use, and certain drug therapies. Regardless of the cause, the complaint of xerostomia warrants an evaluation for hyposalivation. Hyposalivation, which is a measurable decrease in saliva flow, is significant because of its destructive effects on oral tissues and reduced satisfaction with dentures. However, even when occurring in the absence of hyposalivation, complaints of xerostomia need to be addressed.

Currently, clinicians are recommending simple palliative therapies for xerostomia, which may include topical saliva substitutes, oral moisturizers, saliva stimulants in the forms of sprays, gels, gums, lozenges, mouth wash, and/or frequent sips of water. Recent reviews have weak evidence in favor of any particular topical therapy (Shahdad, 2005; Sasportas, 2013; Jose, 2016).

Biotène Moisturizing Mouth Spray is one such widely available over-the-counter (OTC) formulation which can be sprayed directly into the mouth for the relief of xerostomia. Although the spray is recommended empirically, its properties are not fully understood. One of the most important properties is its duration of effect in the mouth (Shahdad et al. 2005; Sasportas et al 2013). For example, how long a typical dose can be expected to last is not currently known. Manufacturers' instructions for the use of Biotène Moisturizing Mouth Spray state, "Spray directly into the mouth, onto the tongue, and spread thoroughly throughout the mouth. Use as required." For clinicians to effectively

advise patients and institutions (e.g. nursing homes), information about expected duration of effect is needed.

2. STUDY DESIGN

2.1. Overview

This double blind controlled randomized crossover study is designed to determine the duration of effect of a single dose of Biotène Moisturizing Mouth Spray. Because no detailed information about the duration of its effect is available now, a pilot study to determine sample size will be completed first. The spray consists of a mixture of starch, polymers, and plant oils which act as humectants to moisturize the oral tissues as well as flavorings that serve as salivary stimulants (Jose et al. 2016). Subjects complaining of a dry mouth will be recruited from the Division of General Dentistry of the Eastman Institute for Oral Health. Potential subjects will be scheduled for a screening appointment during which they will sign an informed consent form, complete a questionnaire about their experience with xerostomia, and then undergo a measurement of unstimulated whole saliva flow rate (UWSFR). Those whose UWSFR is \leq 0.2mL/min. will be admitted to the study and will then be administered a dose of either the experimental or control (water) agents. The unstimulated whole salivary flow rate of 0.2 mL/min is selected because it is widely recognized as the level at which actual mouth dryness occurs (Coulter et al, 2008). Statistical analysis will focus primarily on comparing the duration of action of the two agents but also collecting qualitative information about subjects' experiences with xerostomia and the two agents.

2.2. Rationale for Study Design

Xerostomia is a common oral health problem, with up to 50% of the population affected (Furness et al, 2011). A number of topical agents have been produced to help ameliorate the problem but evidence-based information about their indications and comparative effectiveness is sparse (Furness et al. 2011, Sasportas et al. 2013, Villa et al. 2015, Jose et al. 2016,). This study aims to compare the duration of effect of one widely available topical product (Biotène Moisturizing Mouth Spray) to water for the management of xerostomia. A pilot study is planned initially to determine the sample size for a definitive study. The double-blind design will avoid investigator bias after subjects are randomized to treatment groups.

2.3. Rationale for Dosage

The dosage selected for this investigation is three sprays (0.5 mL) from a primed metered-dose spray bottle identical to what is commercially available to patients. This dose was selected because we feel it simulates the dose a patient with xerostomia would

likely utilize. The spray will be administered by the investigator, [name], (CL) after priming the bottle twice prior to the providing the determined dose.

3. CHARACTERISTICS OF THE RESEARCH POPULATION

3.1. Subject Characteristics

Pilot Study

In order to establish adequate power at an acceptable level of significance for this study, an estimate of the duration of effect of the experimental and control is needed. At this time no such information is available; therefore a pilot study will be completed, as suggested by the study statistician ([name], PhD). Results of the pilot will help determine the minimum number of subjects required for a definitive study. The following describes the characteristics of the population for the pilot study:

- a) **Number of subjects:** A total of 20 subjects enrolled is suggested by the biostatistician. A subject is considered in the total count once informed consent has been obtained and the inclusion criteria met. To account for dropout and disqualification of eligible subjects, 50 subjects will be recruited.
- b) **Gender and age of subjects:** Adults aged 18 years and over will be enrolled with no regard to gender, although it is recognized that xerostomia in the general population is more prevalent in older adults and in females (Fox et al. 1985).
- c) **Racial and ethnic origin:** Subjects will be recruited without regard to race or ethnicity.
- d) **Vulnerable subjects:** Vulnerable subjects (as defined by University of Rochester IRB Criteria) will not be enrolled.

3.2. Inclusion and Exclusion Criteria

- a) Inclusion Criteria:
 - Adults who are in good general health and reply initially affirmatively to the question, “Do you feel that your mouth is too dry and causes you discomfort at times during the day other than on awakening from sleep?” This question is an adaptation of the question used successfully by Jose and others (2016) to recruit study subjects.
 - Adults who are able to communicate easily in English and who are able to demonstrate understanding of the study instructions.
 - Adults who are physically able to perform an unstimulated whole saliva flow rate (UWSFR) test and who produce 0.2 mL/min or less of saliva.
- b) Exclusion Criteria:
 - Adults under the care of a health professional specifically for xerostomia treatment, including those taking prescription systemic parasympathetic medications.

- Adults who regularly “self-medicate” their xerostomia with water or other agents or products designed to treat their xerostomia and are unwilling or unable to cease use of the agent for at least 48 hours prior to the two test visits.
- Adults who are primarily mouth breathers (i.e. mouth breathing secondary to nasal obstruction)
- Adults who cannot consent for themselves or have physical/mental disabilities requiring a caregiver.
- Adults with a known allergy to any of the ingredients in Biotène Spray (eg. dairy allergy)

3.3. Discussion of the Subject Population

The inclusion criteria target the large proportion of the adult population (up to 50%) (Furness et al, 2011) who are generally healthy but complain of a dry mouth. This enrollment strategy focuses on a “real world” dry mouth population who might use these treatments for the daily management of their symptoms. The exclusion criteria are aimed to eliminate factors and conditions that might artificially limit typical saliva flow. Subjects who have unstimulated whole salivary flow rates above the 0.2 mL/min threshold will be excluded to reduce the variation among subjects and minimize the possible participation of those who are unable to discriminate between lower and higher flow rates; this latter group may be studied further in another investigation.

4. SUBJECT IDENTIFICATION, RECRUITMENT, AND CONSENT

4.1. Method Of Subject Identification And Recruitment (See Appendices 1 and 2)

Subjects will be initially identified and recruited at all the dental clinics of the Eastman Institute for Oral Health (EIOH) at the University of Rochester, Rochester, NY, by the strategies described here. Those identified will be assured, from the outset, that neither their clinical care at EIOH nor their healthcare anywhere else in the University Medical Center will be affected by their decision whether or not to take part in the study.

1. Investigators’ patients. Both Drs. [name] and [name] see EIOH patients regularly. They will recruit patients directly from their patient pools by advising them of the study and inclusion and exclusion criteria. They will pose the question regarding discomfort from xerostomia detailed in section 3.2 a) above to any adult patients who appear to meet the inclusion criteria; those who respond affirmatively will be identified as potential subjects. Definitive qualification will follow as the subjects complete the consent process and the UWSFR test.
2. Recruitment posters. Posters will be placed in hallways, near elevators, and within the dental operatories at the clinics and which will indicate that the study is underway. The posters will include the basic inclusion and exclusion criteria and the information that those who are interested should contact [name] by phone

or e-mail; her contact information will be included (Appendix 3). Those who enter the study by this route will be considered to have “self-identified” themselves as potential study subjects.

3. Meetings with dental residents. [name] will meet with her fellow dental residents to explain the study, provide posters, and request their assistance in recruiting potential subjects from among their pool of regular patients.

Potential subjects will be asked to contact the investigator for a screening appointment at the study site and will be offered the consent form (please see next section 4.2 for details.), which includes details of the study to read and consider at their leisure and with others (e.g. family members, their personal dentists). They will be advised that, on completion of both sessions of the study, they will receive \$75 plus parking in appreciation for their time and effort. Persons who meet the inclusion criteria and sign the consent form will be considered recruited for the study.

As subjects qualify for the study, they will be placed, according to a randomization table (Appendix 4), in either one group (Group A) or the other (Group B). If a patient being recruited is found not to meet the inclusion criteria, s/he will be dismissed and the next potential candidate will be evaluated for admission to the study.

Patients will be assured that their regular clinical care will not be affected by their decision to participate or not participate in the study. Similarly, enrolled subjects who withdraw from the study will be assured that they will continue to receive their regular clinical care.

4.2. Process of Consent (Please see draft Consent Form) attached.)

After the initial discussion about the study, the investigator will provide the prospective subject with a paper consent form which describes the study in detail. The subject will be informed that they may undergo temporary discomfort during the study, and so this is a consideration whether or not to participate. As previously described, potential subjects will be given every opportunity to discuss or ask questions of the investigators that occur to them. They will be advised of any anticipated risks and contact information for the investigators and others affiliated with the University who could assist with any problems which might develop and personnel who might carry responsibility for subjects’ safety. The consent form will carry a statement to the effect that subjects may withdraw from the study at any time without affecting their eligibility for dental care or other care at the University and without any other penalty. The subject must give her/his own consent without a caregiver, spouse, or legal guardian. Signed consent forms will be paper documents stored in a locked file cabinet accessible only to the investigator on an electronically locked laboratory floor.

5. METHODS AND STUDY PROCEDURES

5.1.1. Treatment Dosage and Administration.

The methods and study procedures will consist of the following 11 parts which will be completed during a recruitment encounter and two testing visits. (See also Appendices 5 and 6).

Recruitment Encounter

This will be brief and will occur at the time the potential subject volunteers to be considered for the study. (Please see below for details.)

Visit 1

1. Sign consent form (if not completed at Recruitment Encounter.)
2. Update of medical history and recording of blood pressure and pulse.
3. Questionnaire about subject's xerostomia experience.
4. Determination of unstimulated whole saliva flow rate.

The inclusion criteria for the study require that the rate be ≤ 0.2 mL/min. A subject's participation will be terminated at this point if this inclusion criterion is not met.

5. Trial with randomly assigned alternative or experimental agent.
6. Post-test study questionnaire about study agent.

Session 1 is complete at this point. An appointment will now be scheduled for Session 2.

Washout Period

As is usual in studies utilizing a crossover design a "washout period" will be employed in this investigation. The retention time appears to be related to the viscosity of a topical agent for the relief of a dry mouth (Shahdad et al. 2005). Therefore, a washout period of at least 48 hours, to be utilized here, appears to be sufficient to eliminate the effects of a single application of Biotène.

Visit 2

1. Update of medical history and recording of blood pressure and pulse.
2. Determination of unstimulated whole saliva flow rate. Subjects will continue in the study regardless of their salivary flow rate at this point. The mean of the UWSFRs measured at Sessions 1 and 2 will be used in calculations comparing flow rates to duration of action of the two agents. This will be done as a matter of interest in the amount of variation that may exist between the 2 UWSFR measurements.
3. Trial with either control or experimental agent, whichever was not tested in Session 1.
4. Post-study questionnaire about study agent, whichever was not tested in Session 1.

Each of the two testing visits is expected to utilize as much as three (3) hours but may be less, depending mainly on subjects' responses to the test agents. Both sessions will be

scheduled in the time period 830am – 1230pm to control for known variations in daily flow rates.

Detailed descriptions of each part follow here.

Recruitment Encounter

This encounter would commonly occur during or after a routine clinic visit or otherwise after s/he learns of the study. At this time the investigator would read to the potential subject a scripted question plus a limited statement of eligibility. If the investigator continues to feel that the subject may be eligible s/he will be encouraged to sign the consent form. At the potential subject's request s/he may take the consent form for the purpose of further consideration personally or with family, other health professionals, etc. and return it at the first experimental visit. (See Appendix 1 for Scripted Recruitment Statement).

Visit 1

1. Sign consent form if this was not done at the Recruitment Encounter. Update of subject's medical history and measurement of vital signs (blood pressure, pulse, respiration rate, presence and level of any pain.).

2. As also indicated previously, when subjects are initially contacted about the study they will be given a consent form to take with them and consider participation, possibly including discussions with family, health professionals, etc., and then return to the investigator. If any questions exist the investigator will respond and then require that the consent be signed by both the investigator and subject prior to proceeding. A copy of the signed form will be given to the subject and the original retained by the investigator in a locked file in a University facility accessible only to investigators.

3. Survey of Experience with Xerostomia. (Appendix 7)
 A secondary aim of the study is to gather qualitative information about subjects' experiences with xerostomia. A tested 6-item written questionnaire will be administered at this time.(Shahdad et al, 2005) for this purpose. The time needed for completion of this brief questionnaire is estimated at 5 minutes.

4. Determination of Unstimulated Whole Saliva Flow Rate. (UWSFR) (See Appendix 8)
 The purpose of this test is to determine whether or not potential subjects have a rate of not more than 0.2 mL/min. The UWSFR test will be completed in a quiet room with lighting generally at a low level but bright enough to allow for reading. Subjects will be seated in a cushioned chair and encouraged to make themselves as relaxed and comfortable as possible. A pre-weighed plastic disposable drinking cup (+/- 0.01 g) will be given to the subject with instructions to cease the normal process of swallowing when

saliva accumulates but rather allow it to accumulate in the mouth and then drain gently into the cup. The time will be noted by the investigator and, after 15 minutes, the investigator will advise the subject that the test has ended. The investigator will again weigh the cup and saliva and record the weight. One gram will be understood to be approximately equivalent to 1 mL of saliva and the new weight recorded. The weight per minute will be calculated and understood to be the subject's current unstimulated whole saliva flow rate (UWSFR). If the rate is < 0.2 mL/min the subject will be advised that the inclusion criteria for the remainder of the study have been met and that the study will continue. This level was selected as a "cut-off" both because it is the level at which existing literature recognizes genuine mouth dryness to likely exist and also because of our belief that subjects who perceive dryness in the presence of relatively 'normal' salivary flow rates, may be unreliable in their reports of beneficial effects of study agents. Subjects who do not meet the inclusion criteria will be given \$25 in appreciation for their participation to this time and then dismissed.

6. First Test agent.

The subject will then be seated in a quiet dimly lit room and asked to refrain from speaking, including using phones, unless it is essential (e.g. they are feeling badly enough that their participation needs to be paused or stopped). After not less than one (1) minute a visual analog scale (VAS) of dryness will be recorded in response to the question, "How much discomfort are you feeling from your dry mouth?". (See Appendix 9). They will then be administered, by the investigator, a dose of 3 sprays (to the anterior dorsal of the tongue) of the randomly selected experimental or alternative agent with instructions to "spread it around in your mouth." An electronic timer will be started by the investigator at that time. The investigator will be administering the agents after priming the spray bottle twice before aiming the first spray to the anterior dorsal of the subject's tongue. Neither the investigator nor the subject will know the identity of the administered agent.

One minute after the spray a second VAS will be recorded. For every 15 minutes elapsed, the investigator will repeat the question, "How much discomfort are you feeling from your dry mouth?" Subjects' responses will be recorded each time. Subjects will be instructed to stop the timer when they feel that the effect of the administered agent has dissipated completely (Appendix 10).

Studies with other more viscous moisturizing agents have rarely found the duration of effect to be more than two (2) hours. Therefore, the maximum amount of time subjects in this study will be tested is two (2) hours (Jose et al, 2016). The endpoint for each subject, however, will occur the subject feels that the effect of the agent has dissipated; the

duration of effect will be the time between starting the timer and the elapsed time to the endpoint.

6. Survey of Experience with First Test Agent.

A secondary objective of this study is to gather new information about subjects' perceptions of the characteristics of agents designed to relieve xerostomia. However, a review of literature utilizing PubMed and references from other investigations did not reveal a standardized survey tool for this objective. Therefore a new post-test questionnaire about agents designed to ameliorate xerostomia was designed by investigators and will be administered (Appendix 11). This information could be useful in the subsequent full study to help determine whether or not further efforts are needed to mask any potentially noticeable differences between agents being tested. This is a 9-item survey of a variety of characteristics of potential agents. A printed copy of the survey attached to a clipboard and also a black-ink pen will be handed to the subject. The subject will be instructed to circle the best answers and then return. The use here of this questionnaire will constitute a pilot study because it is new and has not yet been validated.

At this time the subject will be given a check for \$25, an appointment for the second visit, and dismissed for the day.

Washout Period

A period of at least 48 hours will be required prior to Visit 2.

Visit 2

1. Update of medical history and recording of blood pressure and pulse.
2. Second sialometry to determine a second UWSFR.
3. Administration of second test agent (which ever was not used in Session 1). Recordings of VAS regarding the feeling of dryness will be made just before and after administration of the test agent and then every 15 minutes in a manner identical to that of Session 1. Subjects will be instructed to stop the timer when they feel the effect of the test agent has dissipated completely; this will mark the endpoint of the duration of effect, which will be recorded.
4. Survey of experience with second test agent.

This will utilize the same survey form used in Session 1 (Appendix 11).

At this point, the subject has completed the required commitment to the study, and will be de-briefed, including being requested to verbally supply any comments they feel might be useful in future studies in which they might participate. Subjects will be offered additional

information and/or referrals to a dry mouth clinic as needed. They will be compensated \$50 plus parking for their participation and dismissed.

(See also Appendices 4 and 5 for flow chart and schedule of activities.)

5.1.2. Amount of agent to be tested. And 5.1.3. Investigational drug/device.

The manufacturer of Biotène Moisturizing Mouth Spray has directions (Appendix 12) printed on the spray bottle stating, “Spray directly into the mouth, onto the tongue, and spread thoroughly inside the mouth. Use as required. Safe to swallow when used as directed.” In an effort to minimize variation in the amount dispensed for this study but to remain essentially consistent with the manufacturer’s directions the investigator will assume the following calibration protocol for each subject:

1. Weigh the empty cup to be used for collection of whole saliva.
2. Prime the spray bottle by squeezing firmly at least twice, toward a sink or bucket. This “spray sample” will then be discarded.
3. Using the identical technique, three sprays will then be collected in a second empty cup and weighed. This will serve as a “calibration sample.” This sample will then be discarded but the empty cup retained.
4. The investigator will then direct three sprays to the anterior dorsal of the tongue. Utilizing a total of three sprays is intended to mimic what a xerostomic patient likely would do. Having the investigator, instead of the subject, administer the agent is expected to make the amount of agent expressed be generally uniform among subjects.
5. The same cup will be handed to the subject and will be used for collection of the sample of whole saliva over a period of 15 minutes.

The organization and administration of the test agents will be completed in the laboratory of [name], Pharm D, Manager of Investigational Drug Services (IDS) here at the University. Each bottle of test agent (either Biotène Dry Mouth Moisturizing Spray or sterile water) will be appear in identical spray bottles. The possibility exists that the investigator or subject may notice the scent and viscosity differences between the different agents, however this will unlikely impact the outcome measures. To assess the impact of these differences, the post-test questionnaire (Appendix 11) will ask subjects if they think they received the moisturizing spray or the alternative (sterile water). The spray bottles will be unlabelled except for a unique number which identifies the contents to IDS laboratory and the statistician. The true identities of the bottles will be unknown to the investigator and the subjects. The contents of the test agent will be linked to each subject through a randomization process completed by IDS.

A recent study (Jose et al, 2016) sponsored by the manufacturer (GlaxoSmithKine) of Biotène spray investigated the comparative effect of 3 of its products with 2 hours as the primary endpoint. Since xerostomia lasting longer than 2 hours may be uncomfortable, demonstrating that an agent provides relief close to this time frame would have potential therapeutic and commercial value. Although the study design was different, 49.5% of subjects reported that the spray was good, very good, or excellent at “relieving the discomfort of dry mouth” 2 hours after use of the spray. A previous study (Shahdad et al. 2005) also discovered that most subjects achieved relief utilizing topical agents after 2 hours. In this study involving a Biotène gel, it was found that the viscosity is positively correlated to the retention time of the agent (Shahdad et al. 2005). Therefore, we expect the less viscous experimental spray to have a shorter retention time than the expected 2 hours. Therefore, 2 hours will be defined as the maximal endpoint in this study. We expect that the crossover design and qualitative measures will aid health care providers and patients to derive benefit from Biotène Moisturizing Mouth Spray or water.

This crossover study will employ a washout period of 48 or more hours. The dose being administered to a subject is small, and the retention time is related to the viscosity of a topical agent for the relief of a dry mouth (Shahdad et al. 2005). Therefore, a washout period of at least 48 hours appears to be sufficient to eliminate the effects of a single application of Biotène.

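### Section 5.1.2 has the masked investigator collect and weigh a cup of the agent before dosing, and leaves unclear which cup is used for saliva and when it is collected

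*Combined protocol and SAP*

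**What the plan says.** Section 5.1.2 (printed jointly with 5.1.3) lists five steps, introduced by "the investigator will assume the following calibration protocol for each subject". The stated aim is to make the quantity dispensed less variable.

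- Step 1: the empty cup meant for whole saliva is weighed.
- Step 2: "Prime the spray bottle by squeezing firmly at least twice, toward a sink or bucket".
- Step 3: "three sprays will then be collected in a second empty cup and weighed". Then: "This sample will then be discarded but the empty cup retained".
- Step 4: "The investigator will then direct three sprays to the anterior dorsal of the tongue".
- Step 5: "The same cup will be handed to the subject and will be used for collection of the sample of whole saliva", over 15 minutes.

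On masking, section 5.1.1 (First Test agent) says: "Neither the investigator nor the subject will know the identity of the administered agent". The text after step 5 concedes that investigator or subject might notice differences in smell or viscosity, judges this unlikely to affect outcomes, and relies on a questionnaire item in which the subject guesses the agent (Appendix 11).

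On order, section 5.1.1 puts the saliva flow test (UWSFR) before the test agent at both visits. On dose, section 2.3 says: "The dosage selected for this investigation is three sprays (0.5 mL) from a primed metered-dose spray bottle". Sections 2.3, 5.1.1 and 8.2 mention priming and dosing but no calibration sample.

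**The concern.** Three things are at stake.

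**Masking.** The person who collects and weighs the sample also gives the dose, starts the timer and puts the discomfort question every 15 minutes. Section 8.1 lists sunflower oil, milk protein extract and glycols in the active spray; the comparator is water. In a two-period crossover, recognising one agent identifies the other period too. Only subjects are asked to guess, so unmasking of the investigator would go unrecorded.

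**Dose information.** The weighed sprays are thrown away and the administered ones are not weighed. No tolerance, action limit or analysis is attached to the calibration weight, and the sample data forms in Appendices 8 and 10 have no field for it.

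**Saliva measurement.** UWSFR decides eligibility at Visit 1, and its two-session mean enters the comparison of flow with duration. Step 5 leaves both the cup and the timing open to a reading in which agent is weighed as saliva.

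**Working it through.** The plan gives no figure of its own to reproduce here.

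**1. What the investigator handles.** Section 2.3 gives 0.5 mL for three sprays, so 0.5/3 = 0.167 mL per spray. One full sequence is at least 2 priming + 3 calibration + 3 dosing = 8 sprays, or 8 × 0.167 = 1.33 mL. Without step 3 it is 5 sprays. Step 3 therefore adds three sprays and is the only step in which the agent is pooled in a container and weighed.

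**2. How well the sample stands in for the dose.** Assume independent sprays with per-spray coefficient of variation c (not in the documents) and mean m. The difference between two three-spray totals has SD √6·c·m. Divided by the dose 3m, this is c·√(2/3).

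| Assumed c | SD of (sample − dose), % of dose |
|---|---|
| 5% | 4.1% |
| 10% | 8.2% |
| 20% | 16.3% |

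**3. What bottle weighing would give.** Section 5.1.1 states ±0.01 g, for the saliva cup only. Assume that a balance of that precision takes the filled bottle and that density is near 1 g/mL, so the nominal dose is 0.5 g. The error of a difference of two weighings is then:

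- in quadrature: √2 × 0.01 = 0.014 g, and 0.014/0.5 = 2.8%;
- worst case: 2 × 0.01 = 0.02 g, and 0.02/0.5 = 4%.

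**4. Which cup, and when.** Setting the passages side by side:

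| Place | Cup | Timing of saliva collection |
|---|---|---|
| 5.1.2 step 1 | a cup weighed empty and designated for saliva | not stated |
| 5.1.2 step 3 | a second cup, holds agent, emptied and kept | not applicable |
| 5.1.2 step 5 | the same cup, without saying which | listed after dosing |
| 5.1.1 Visits 1 and 2 | a pre-weighed disposable cup (Visit 1 detail) | before the test agent |

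The nearest earlier cup to step 5 is the one kept in step 3; the cup designated by purpose is the one in step 1. The wording settles neither. The order in step 5 also cannot be squared with Visit 1, where participation ends before any agent is given if the flow criterion is not met.

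**5. What contamination would do, if it occurred.** Over 15 minutes, a mass r of agent counted as saliva adds r/15 to the rate, provided the cup is not re-weighed after emptying. At the 0.2 mL/min cut-off the collection is 0.2 × 15 = 3.0 g. For an assumed r of 0.02 to 0.10 g, the rate rises by 0.0013 to 0.0067 mL/min, which is 0.7 to 3.3% of the cut-off. If a full 0.5 g ended up in the collection, the rise would be 0.5/15 = 0.033 mL/min, or 17%. These are conversions from assumed masses and do not estimate what would happen.

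**The case against.** The other side has good arguments, and several stand.

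- **A reader might infer that saliva readings are contaminated with agent.** The documents do not show this. Step 1 designates a separate cup before any agent is sprayed, and section 5.1.1 tests saliva before dosing. On that reading there is no residue. What stands is an ambiguity and a conflict of order. In addition, any error entering the two-session mean cannot differ by agent, because each subject contributes one session with each.
- **A reader might infer that bottle weighing would secure the masking.** It would not. Priming, scent and the sprays to the tongue remain. Bottle weight could itself be a cue: at an assumed density 1 to 5% above water, a 45 mL fill (the size in section 8.1) differs by 0.45 to 2.25 g.
- **A reader might infer that the plan claims to measure the delivered dose and fails.** It makes no such claim. Step 3 is called a calibration sample and can serve to check output before the subject is dosed. Bottle weighing finds a faulty spray only afterwards, and records mass emitted, not mass retained in the mouth.
- **A reader might infer that the pool is taken before every dose and stays on view.** The text says per subject, leaves open whether that means each visit, and has the sample discarded. Only the emptied cup is kept.
- **The risk is partly acknowledged, and the endpoint is the subject's.** The subject stops the timer, so an unmasked investigator could act only indirectly, through the repeated questioning. Nothing in the documents allows that effect to be sized.

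These arguments limit the claim. They do not justify having a masked person pool and weigh the agent for a figure with no stated use.

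**Conclusion.** The point holds as a modest, cheaply corrected weakness in procedure.

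- Step 3 adds an avoidable exposure of the masked investigator beyond the one section 5.1.2 admits. Its effect on masking or on duration cannot be derived from the documents.
- The sprays given to the subject are never weighed. This is a limitation of the plan; it does not contradict any stated purpose.
- Step 5 is ambiguous about the cup and conflicts with section 5.1.1 about the order. If the agent cup is used, or saliva is collected after dosing, UWSFR can be biased upward. The size is unknown.
- Bottle weighing would give emitted mass to about ±0.014 to 0.02 g, 3 to 4% of 0.5 g, subject to the density and balance assumptions above.

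**What to change.** 1. In section 5.1.2, state that saliva is collected only in the pre-weighed cup of step 1, and that this cup never holds agent.
2. Reconcile the position of saliva collection in step 5 with the visit sequence in section 5.1.1.
3. Replace the cup sample in step 3 with a weighing of the primed bottle immediately before and after the planned sprays. Record the difference as emitted mass and add a field for it to the data form. The planned number of sprays is unchanged. Confirm first that the balance takes the filled bottle at ±0.01 g.
4. State the remaining limits: priming, scent and possibly bottle weight are still cues; output is no longer checked before dosing; and emitted mass is not mass retained in the mouth. Recording the investigator's guess of the agent at each visit, and having unblinded pharmacy staff do the bottle weighings where practicable, would help further.

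The core change costs almost nothing: two bottle weighings in place of the calibration weighing, one form field and a few lines of text. The optional help from pharmacy staff would need some of their time.
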